5.1 Inclusion Criteria

Participants are eligible to be included in the study only if all the following criteria apply:

Category	Criterion
Age	1. Are between 18 and 55 (inclusive) years of age at the time of signing the informed consent.
Type of Participant and Disease Characteristics	2. Are overtly healthy as determined by medical evaluation, including no clinically significant abnormality identified on physical examination or laboratory evaluation and no active clinically significant disorder, condition, infection, or disease that would pose a risk to participant safety or interfere with the study evaluation, procedures, or completion.
Weight	3. Have a body weight within 50.0 and 100.0 kg (inclusive) and BMI within the range 19.0 and 30.0 kg/m ² (inclusive).

Category	Criterion
Sex and Contraception/Barrier Requirements	
4.
 
 • Male 
 ○ No contraception and barrier requirements needed. • Female 
 ○ Is not a woman of childbearing potential (Appendix 3). 
Note: Study to include approx. 30% or more of each sex

Informed Consent	5. Are capable of giving signed informed consent, as indicated in Appendix 2 , which includes compliance with the requirements and restrictions listed in the ICF and this protocol.
Smoking	6. Are stable nonsmokers for at least 3 months preceding the first administration of study intervention.

5.2 Exclusion Criteria

Participants are excluded from the study if any of the following criteria apply:

Category	Criterion
Medical Conditions	
1. History or presence of clinically relevant respiratory, gastrointestinal, renal, hepatic, hematological, lymphatic, neurological, cardiovascular, musculoskeletal, genitourinary, immunological, dermatological, connective tissue, psychiatric (due to rare risk of hallucinations, agitation and activation of psychosis), and other diseases or disorders, and epilepsy, as determined by medical evaluation.
 
2. Individuals with diagnosis of hemochromatosis, Wilson's disease, alpha 1 antitrypsin deficiency, or any other chronic liver disease including Gilbert's disease will be excluded from the study.
 
Prior history of cholecystectomy or splenectomy, and any clinically relevant surgery within 6 months prior to the first administration of study intervention.
 
3. History of any malignancy.
 
4. History of seizures.

Category	Criterion
	5. History of pharmacologically treated psychiatric disease.
	6. History of chronic or recurrent acute infection or any bacterial, viral, parasitic or fungal infections within 30 days prior to Screening and at any time between Screening and admission, or hospitalization due to infection within 6 months prior to the first administration of study intervention.
	7. History of shingles within 12 months prior to Screening.
	8. History of drug hypersensitivity (e.g. quinolones and ascertained or presumptive allergy/hypersensitivity to the active drug substance and/or formulation ingredients); history of serious allergic reactions leading to hospitalization or any other hypersensitivity reaction in general including contact hypersensitivity to ECG electrodes, which may affect the safety of the participant and/or outcome of the study per the Investigator's discretion.
	9. History of alcoholism or drug abuse within 2 years prior to the first administration of study intervention, or positive for drugs of abuse, nicotine/cotinine or alcohol by the laboratory assays conducted during Screening and Study Day -1.
	10. History of residential exposure to tuberculosis, or a positive QuantiFERON® test within 4 weeks prior to or at the time of Screening.
	11. Positive for a) hepatitis B surface antigen, hepatitis B core antibody, hepatitis C antibody, or human immunodeficiency virus I and II tests at Screening; b) SARS CoV-2 at Screening or Study Day -1.
	12. Any condition, including findings in the laboratory tests, medical history (e.g. heart failure, hypokalemia, family history of Long QT Syndrome), or other Screening assessments, that in the opinion of the Investigator constitutes an inappropriate risk or a contraindication for participation in the study or that could interfere with the study's objectives, conduct, or evaluation.

Category	Criterion
	
13. Administration of live vaccines or live-attenuated virus vaccines within 3 months prior to Screening. Administration of other types of vaccines (e.g. SARS-CoV-2 vaccines) is allowed until 42 days before the first administration of study intervention, thereafter it is prohibited until the end of the study.
 
Note: In case of clinical symptoms, the participant should be symptom-free for at least 1 week prior to the first administration of study intervention.

Prior/Concomitant Therapy	
14. Moderate or strong inhibitors or inducers of CYP3A4/5 or P-gp within 4 weeks prior to the first administration of study intervention.

	
15. Use of any prescribed medicine or over-the-counter drug or dietary supplement, including herbal remedies, vitamins, and minerals, antacids and dietary supplements such as fish oils within 2 weeks or 5 times the half-life of the respective drug, whichever is longer, prior to the first administration of study intervention.
 
Occasional paracetamol (acetaminophen) up to 2 g per day is permitted.

Prior/Concurrent Clinical Study Experience	
16. Use of any investigational drug in any clinical study within 60 days prior to Study Day 1 administration, or have used an experimental monoclonal antibody within the past 1 year prior to Study Day 1, or have participated in a study evaluating a BTK inhibitor within 60 days, or are on extended follow-up in a clinical study, even if last administration of a study intervention was more than 60 days ago, or 5 half-lives of the investigational drug, whichever is longer, prior to the first administration of study intervention.

Diagnostic Assessments	
17. Medical history and physical examination results that include any ongoing clinically relevant findings as judged by the Investigator.

Category	Criterion
	
18. Clinically relevant findings (excluding minor, not clinically relevant excursions from normal ranges, as judged by the Investigator) at Screening in biochemistry, hematology, coagulation, and urinalysis examinations for the age of the participant, as judged by the Investigator:
 
• Alanine aminotransferase, aspartate aminotransferase: above ULN• Creatinine: above normal limits• Absolute lymphocyte count, absolute neutrophil count: below limit of reference range.• Amylase and lipase above normal ranges, minor deviations are allowed, if not clinically relevant.• Abnormal, low levels of potassium levels
	
19. Estimated glomerular filtration rate according to the Chronic Kidney Disease Epidemiology Collaboration Creatinine Equation (2009) < 90 mL/min at Screening. In case of a borderline result between ≥ 80 and < 90 mL/min, Cystatin C will be determined in addition, and the participant will only be included if the Cystatin C value is below the upper limit of normal.

	
20. Semi-supine systolic blood pressure > 140 mmHg or < 90 mmHg, diastolic blood pressure > 90 mmHg or < 50 mmHg, and pulse rate > 90 or < 50 bpm at Screening. Any abnormal blood pressure results may be repeated once and if the repeat result is within the normal range, it is not considered to have met the exclusion criterion.

	
21. 12-Lead ECG showing a QT interval corrected for heart rate according to Fridericia's formula (QTcF) > 450 ms, PR > 215 ms, or QRS > 110 ms at Screening.

	
22. Any other abnormal laboratory results that the Investigator believes should preclude the participant's participation in the study.

Other Exclusions	
23. Consumption of an average weekly alcohol intake of > 14 units/week for men or > 7 units/week for women. 1 unit (12 g) of alcohol equals $\frac{1}{2}$ pint (285 mL) of beer or lager, 1 glass (125 mL) of wine, or $1/6$ gill (25 mL) of spirits.

Category	Criterion
	24. Contraindication to moxifloxacin (refer to approved product information moxifloxacin).
	25. Excessive consumption of xanthine-containing food or beverages (> 5 cups of coffee a day or equivalent) or inability to stop consuming caffeine, from 48 hours prior to study intervention administration until after collection of the final PK sample in each period.
	26. Consumption of alcohol from 48 hours prior to first administration of study intervention.
	27. Herbal supplements including, but not limited to, St. John's wort (hypericum perforatum), grapefruit, Seville oranges, cranberries, or juices of these fruits within 14 days prior to the first administration of study intervention.
	28. Donation or loss of more than 450 mL of blood in the 60 days prior to the first administration of study intervention, donation of plasma from 2 weeks prior to the first administration of study intervention, or platelets from 6 weeks prior to the first administration of study intervention.
	29. Travel to a country with a high prevalence of tropical diseases within 3 months prior to the first administration of study intervention.
	30. Inability to communicate reliably with the Investigator or considered by the Investigator to be unable to or unlikely to cooperate with the requirements of the study.

5.3 Lifestyle Considerations

5.3.1 Meals and Dietary Restrictions

- Participants will abstain from consuming Seville oranges, grapefruit or grapefruit juice, pomelos, exotic citrus fruits, grapefruit hybrids, or fruit juices from these fruits from 14 days before the start of study intervention until after the final dose.
- Participants will receive standardized meals on Day -1 of each period at customary times.
- On Day 1 of each period the participants will be fasting (no food, no beverages, only water is allowed) from at least 10 hours before and until 4 hours after drug administration. Ingestion of water between 1 hour predose and until 1 hour postdose will not be allowed. 4 hours after drug

administration, a standardized lunch will be served. An afternoon snack will be provided approximately 8 hours and dinner approximately 12 hours postdose.

5.3.2 Caffeine, Alcohol, Tobacco, and Cannabinoid

- During each dosing period participants will abstain from ingesting caffeine- or xanthine-containing products (e.g. coffee, tea, cola drinks, and chocolate) for 48 hours before the start of dosing until after collection of the final PK sample.
- In this study the consumption of alcohol is not allowed from 48 hours prior to first administration of study intervention (see Section 5.2) until after collection of the final PK sample.
- During the study, participants will abstain from THC or cannabinoid-containing products for 2-weeks before the start of dosing until after collection of the final PK sample.
- Participants who use tobacco products will be instructed that use of nicotine-containing products (including nicotine patches) will not be permitted from at least 3 months preceding Screening until after the final follow-up visit.

5.3.3 Activity

Participants will abstain from strenuous exercise for 3 days before each blood collection for clinical laboratory tests and PK samples. Participants may participate in light recreational activities (e.g. watching television or reading).

5.4 Screen Failures

Individuals who do not meet the criteria for participation in this study (screen failure) may not be rescreened with the following exceptions:

- The participant successfully passed the screening procedures but subsequently could not start the study on schedule.
- Initial screening occurred too early to complete the required washout period after any prior therapy.
- The participant was not included due to transient reasons (e.g., an infection at the time of screening).
- Minor (not clinically relevant, as judged by the principal investigator) deviations from the in-/exclusion criteria at the previous screening may entitle the participant for rescreening.

Rescreening will be limited to 2 rescreenings per participant.

If an individual is to be rescreened, signature of a new ICF will be required.

5.5 Criteria for Temporarily Delaying Administration of Study Intervention

Not applicable.

6 Study Intervention(s) and Concomitant Therapies

Study intervention is any investigational intervention(s), marketed product(s), placebo, or medical device(s) intended to be administered to a study participant per the study protocol.

6.1 Study Intervention(s) Administration

Study Intervention(s) Administered

Intervention Label	Placebo	Moxifloxacin	Evobrutinib	Evobrutinib
Intervention Name	Placebo	Moxifloxacin	Evobrutinib	Evobrutinib
Intervention Description	Participants will receive an oral solution of placebo	Participants will receive an oral 400 mg dose of moxifloxacin	Participants will receive an oral 45 mg dose of evobrutinib	Participants will receive an oral 225 mg dose of evobrutinib
Type	Drug	Drug	Drug	Drug
Dose Formulation	Solution	Tablet	Solution	Solution
Unit Dose Strength(s)	N/A	400 mg	45 mg	225 mg
Dose	Fasted	400 mg (fasted)	45 mg (fasted)	225 mg (fasted)
Dosage Regimen	Single dose	Single dose	Single dose	Single dose
Route of Administration	Oral	Oral	Oral	Oral
Use	Placebo-experimental	Positive control	Experimental	Experimental
IMP or NIMP/AxMP	IMP	IMP	IMP	IMP
Sourcing	Will be provided by Nuvisan GmbH.	Will be provided by Nuvisan GmbH, commercial	-	-

		product from German market.		
Supplier	-	-	Merck Healthcare KGaA; The powder in bottle formulation and the oral solution will be manufactured by Nuvisan.	Merck Healthcare KGaA; The powder in bottle formulation and the oral solution will be manufactured by Nuvisan.
Packaging and Labeling	Study intervention will be provided in bottles. Each bottle will be labeled per country requirement. Additional details of packaging and labeling of study intervention will be defined in a separate IMP Handling Manual.	Study Intervention will be provided in the original, commercial packaging. Commercial blisters and original folding cartons will be labeled as per country requirement.	Study Intervention will be provided in bottles. Each container will be labeled per country requirement. Additional details of packaging and labeling of study intervention will be defined in a separate IMP Handling Manual.	Study Intervention will be provided in bottles. Each container will be labeled per country requirement. Additional details of packaging and labeling of study intervention will be defined in a separate IMP Handling Manual.

Study Arm(s)

Arm Name	Placebo: double-blind period	Moxifloxacin: 400 mg open-label period	Evobrutinib: 45 mg double-blind period	Evobrutinib: 225 mg double-blind period
Arm Type	Placebo-experimental	Active control	Experimental	Experimental
Arm Description	Single dose	Single dose	Single dose	Single dose
Associated Intervention Labels	Placebo	Moxifloxacin	Evobrutinib	Evobrutinib

- Evobrutinib and placebo solution will be administered after reconstituting API (or placebo) in 100 mL buffer. A second bottle of buffer will be used to rinse the bottle with reconstituted API (or placebo) twice (50 mL each time). The participants will then receive 40 mL of water to reach a total volume of 240 mL. Further details are provided in the IMP handling manual.
- All treatments will be administered following an overnight fast (10 h). Subjects will not be allowed any liquid from 1 h predose until 1 h postdose, except for the 240 mL water and buffer required to consume the dose with. Subjects will remain fasting until 4 h postdose.
- To mask the taste of the active compound, both the active compound and placebo will contain orange flavor to allow identical taste. The placebo oral solution will be matched for appearance and volume in order to maintain the blind.
- Moxifloxacin dose will be administered together with a total amount of 240 mL water in a standing position.

6.2 Study Intervention(s) Preparation, Handling, Storage, and Accountability

The Investigator, institution, or the head of the medical institution (where applicable) is responsible for study intervention accountability, reconciliation, and record maintenance (i.e. receipt, reconciliation, and final disposition records).

- Upon receipt of the study intervention(s), the Investigator or designee will confirm appropriate temperature conditions have been maintained during transit and any discrepancies are reported and resolved before use. Also, the responsible person will check for accurate delivery. Further guidance and information for study intervention accountability are provided in the IMP Handling Manual.
- Only participants enrolled in the study may receive study intervention(s) and only authorized site staff may supply it. All study intervention(s) will be stored in a secure, environmentally controlled, and monitored (manual or automated) area, per the labeled storage conditions, and with access limited to the Investigator and authorized site staff.
- Dispensing will be recorded on the appropriate accountability forms so that accurate records will be available for verification at each monitoring visit.
- Study intervention(s) accountability records at the study site will include the following:
 - Confirmation of receipt, in good condition and in the defined temperature range.
 - The inventory provided for the clinical study and prepared at the site.
 - The dose(s) each participant used during the study.
 - The disposition (including return, if applicable) of any unused study intervention(s).
 - Dates, quantities, batch numbers, medication numbers, expiry dates, and the participant numbers.
- The Investigator site will maintain records which adequately documents that participants were provided the doses specified in this protocol, and all study intervention(s) provided were fully reconciled.

- Unused study intervention(s) will not be discarded or used for any purpose other than the present study. No study intervention that is dispensed to a participant may be re-dispensed to a different participant.
- A Study Monitor will periodically collect the study intervention(s) accountability forms.
- Further guidance and information for the final disposition of unused study intervention(s) are provided in the IMP Handling Manual.

6.3 Measures to Minimize Bias: Study Intervention Assignment and Blinding

6.3.1 Study Intervention Assignment

Study using Pre-Coded Randomization provided to site	
On Study Day 1 participants will be assigned a unique number (randomization number) in ascending numerical order. The randomization number encodes the participant's assignment to one of the 4 treatment sequences of the study, per the randomization schedule generated prior to the study by Nuvisan GmbH CTS Department.
 
• Sequence 1: A-B-C-D• Sequence 2: B-D-A-C• Sequence 3: C-A-D-B• Sequence 4: D-C-B-A 
A, B, C, and D are used to denote placebo (solution, fasted), moxifloxacin 400 mg (tablet, fasted), evobrutinib 45 mg (solution, fasted) and evobrutinib 225 mg (solution, fasted), but not necessarily in that respective order.

---	---

Each participant is identified by the study site's unique participant identification code (Nuvisan GmbH identification code). After informed consent procedure, every participant is given a screening number. Only participants who comply with all selection criteria (Sections 5.1 and 5.2) can be included into the study.

The Investigator will keep a record relating the participant numbers (Nuvisan GmbH identification code, screening and randomization number) and the names of all participants who have given their informed consent, to allow easy checking of data in participant files, when required. This record will also include the date of participant's study enrollment and completion, as well as participants who could not be assigned to study intervention for whatever reason.

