1.2 Schema

^a End of Treatment assessment

Treatment A, B, C, and D are used to denote placebo (solution, fasted), moxifloxacin 400 mg (tablet, fasted), evobrutinib 45 mg (solution, fasted) and evobrutinib 225 mg (solution, fasted), but not necessarily in that respective order. The assignment of actual treatments to the labels will be made when generating the randomization list.

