2.3.3 Overall Benefit: Risk Conclusion

Risk minimization measures routinely implemented in early phase clinical studies are considered adequate, including exclusion criteria (see Sections 5.1 and 5.2), adequate biochemical and hematology laboratory monitoring (see Section 8.2.4), and observation of vital signs and ECGs (see Sections 8.2.2 and 8.2.3). Participants will be admitted to the study site for the duration of the study to allow continuous safety monitoring. Considering the measures taken to minimize risk to participants in this study, the potential risks identified in association with evobrutinib and moxifloxacin are justified in healthy participants.

3 Objectives and Endpoints

Objectives	Endpoints	Ref. #
Primary		
To evaluate whether evobrutinib administered as a single oral dose (as solution) of 45 mg or 225 mg prolongs QT/QTc in comparison to placebo control	ΔΔQTcF (placebo-corrected change from baseline QTcF) for evobrutinib; with concentration-QTc analysis as primary analysis	1
Secondary		
To demonstrate QTc assay sensitivity	ΔΔQTcF (placebo-corrected change from baseline QTcF) for moxifloxacin	2
To assess the safety and tolerability of evobrutinib	Nature, occurrence, and severity of TEAEs Absolute values and changes in safety laboratory tests Vital signs assessed from time of first dose to end of study participation Single 12-lead ECGs evaluated by Investigator	3
To assess the effect of evobrutinib on other ECG parameters	QT, QTcB, QTcl, PR, QRS, RR, HR, cardiologist assessment including T-wave morphology, and U-wave.	4
To determine the PK of evobrutinib and its major metabolite at 45 mg and 225 mg oral dose (solution) under fasting conditions and moxifloxacin at 400 mg oral dose	AUC ₀₋₂₄ , AUC _{0-∞} , C _{max} , and t _{max} for evobrutinib and major metabolite AUC ₀₋₂₄ , AUC _{0-∞} , C _{max} , and t _{max} for moxifloxacin	5

4 Study Design

This is a Phase 1, single-center, randomized, double-blinded, placebo- and positive-(moxifloxacin) controlled, single-dose, 4-period crossover thorough QT study. There will be a at least 7-day washout period between successive doses. **CCI**

Eligible participants will be randomized to 1 of 4 treatment sequences in which each of the 4 treatments will be administered sequentially during 4 treatment periods. The 4 treatments are:

- Therapeutic dose, double-blind: single oral dose of evobrutinib (45 mg) solution, administered under fasted conditions;

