- Supratherapeutic dose, double-blind: single oral dose of evobrutinib (225 mg) solution, administered under fasted conditions;
- Placebo control, double-blind: single oral dose of placebo solution, administered under fasted conditions;
- Positive control, open-label: single oral dose of 1 moxifloxacin tablet (400 mg), administered under fasted conditions.

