6.3.2 Blinding

Blinding Method

Randomization codes will be kept strictly confidential, accessible only to authorized staff (i.e. randomization statistician, unblinded reconstitution team, bioanalytical laboratories responsible for analyses of the PK samples and unblinded monitor), until the time of unblinding. All other study-related individuals, ancillary site staff, clinical research associates/monitors, the Investigator, Sponsor, ECG core lab, and clinical research organization staff will remain blinded to study intervention.

Since moxifloxacin will be administered open-label, and evobrutinib and placebo administered double-blinded, the treatment sequences will not be displayed in this protocol. Placeholders ('Treatment A', 'Treatment B', 'Treatment C', and 'Treatment D') will be used to refer to the study interventions. Only authorized staff mentioned above will be aware of the sequences actually used.

The procedures of database lock and unblinding statistical analyses will be documented in the Data Management Plan and Unblinding Plan.

Confirmation of the Indistinguishability of the Study Interventions: evobrutinib and placebo solutions will be identical in volume and appearance.

The analytical laboratories responsible for analysis of the PK samples will be unblinded to study treatment codes to enable sample testing of evobrutinib and moxifloxacin prior to database lock. Masked participant identifiers will be used to support association of PK data with treatment codes while preventing association of treatment codes with any other clinical data, such as safety and clinical response data.

Evobrutinib and moxifloxacin information that would unblind the study participants will not be reported with participant identifiers to investigative sites or blinded personnel until the study has been unblinded.

Assignment Method Retention

Unblinding may be done in the event of an emergency necessary for participant safety or the reporting of SUSARs using code break envelopes provided to the site by the CTS department.

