6.3.3 Emergency Unblinding

In an emergency, the Investigator is solely responsible for determining if unblinding of a participant's study intervention assignment is warranted. Participant safety is always the first consideration in this decision. If the Investigator decides that unblinding is warranted, the Investigator makes every effort to contact the Sponsor prior to the unblinding, unless this could delay emergency treatment. The Sponsor will be notified within 24 hours after unblinding. The Investigator will provide the Sponsor the reason for unblinding without revealing the study intervention, except to the designated global patient safety representative via the Emergency

Unblinding Notification Form. The date of and reason for unblinding will be recorded in the source documents and CRF. Contact information for unblinding in an emergency is given on the participant emergency card provided to each participant, as noted in [Appendix 2](#).

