8.4.3 Electrocardiograms

In this study, ECGs will be recorded using standard 12-lead ECG devices and 12-lead Holter recorders for the following purposes:

- Check of eligibility of a participant for the study during screening using standard 12-lead ECG machines (single ECGs).
- Immediate safety assessment at the site using safety single 12-lead ECGs that are being printed from the Holter recordings.
- Extraction of triplicate 10 s ECGs from continuous Holter recordings for central evaluation and statistical analyses of possible drug effects on cardiac safety parameters.

The standard ten seconds 12-lead ECGs will be recorded by devices (CardioPerfect, Hillroom, Chicago, USA) supplied by the site at times indicated in the Flow Chart. These ECGs will be acquired using Goldberger/Einthoven and Wilson leads in supine position (small pillow under head allowed) and after a rest for at least 15 min. The devices will print the ECGs for immediate evaluation by the investigator or his/her designee. The following automatically calculated parameters will be used: Ventricular rate, PR interval, QRS duration, QT interval (uncorrected) and QTcB and QTcF.

The evaluation by the Investigator includes an overall assessment (normal, description of abnormality including clinical relevance) which will be entered into the eCRF system.

The 12-lead Holter ECGs will be recorded using devices (CM3000 or Seer 12, getemed AG, Berlin, Germany), supplied by the ECG core lab (nabios GmbH, Munich, Germany). All devices will be tested prior to shipment and installed at the site. An on-site training will be performed for the site staff. Details of the ECG recordings and data transfer procedure will be supplied in manuals.

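### Does one masked four-sequence square with open-label moxifloxacin need replacing, because a code break for one participant can reveal the order of others?

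*Protocol*

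**What the plan says.** Protocol Section 4: "Eligible participants will be randomized to 1 of 4 treatment sequences". Section 6.3.1 prints the sequences as A-B-C-D, B-D-A-C, C-A-D-B and D-C-B-A, and says that the randomization number encodes the "assignment to one of the 4 treatment sequences of the study". The letters are masked. Section 1.2: "The assignment of actual treatments to the labels will be made when generating the randomization list".

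Three of the treatments are solutions. The fourth is described in Section 4 as "Positive control, open-label: single oral dose of 1 moxifloxacin tablet (400 mg), administered under fasted conditions". Section 6.3.2 sees the difficulty this creates: "Since moxifloxacin will be administered open-label, and evobrutinib and placebo administered double-blinded, the treatment sequences will not be displayed in this protocol".

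On breaking the blind, Section 6.3.2 says "Unblinding may be done in the event of an emergency necessary for participant safety or the reporting of SUSARs using code break envelopes", and the envelopes are provided to the site. Under Section 6.3.3, in an emergency "the Investigator is solely responsible for determining if unblinding of" a participant's assignment is warranted. Neither section says whether an envelope shows the whole sequence or one period, and neither mentions what a break for one participant might reveal about others.

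**The concern.** In the printed square each letter occurs once in every period, so seeing in which period a participant takes the tablet identifies that participant's sequence group. The one thing still hidden is the key from letters to treatments, and that key is common to all participants. Anything that reveals the key therefore reveals the evobrutinib and placebo order of everyone whose moxifloxacin period has been seen. A code-break envelope for one participant could do this.

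The exposed judgements would be those made at this single centre. Under Protocol Appendix 4 the Investigator grades adverse-event intensity and judges causality. For the standard ECGs (Section 8.4.3), "The evaluation by the Investigator includes an overall assessment". SAP Section 15.1.1 tabulates evobrutinib-related and placebo-related TEAEs, and SAP Section 15.5.1 tabulates the Investigator's ECG interpretation by study intervention. A break is most likely to follow a safety event, when unbiased judgement of later events in other participants matters most.

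**Working it through.** The documents give no figure on this point, so there is none to reproduce. The inputs are the four printed sequences (Protocol 6.3.1), one common key (1.2) and the open-label tablet (4, 6.3.2). Write P for placebo, M for moxifloxacin, L for 45 mg and H for 225 mg.

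**Possible designs.** There are 4! = 24 keys. Relabelling by any of the four sequences returns the same set of sequences, so the 24 keys give 24 / 4 = 6 distinct designs. Each of the 24 possible orders lies in exactly one design, and within each design every moxifloxacin period belongs to exactly one sequence.

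**No break.** For a participant with a known moxifloxacin period, all 3! = 6 orders of P, L and H remain. The best guess is 1/6 for the order and 1/3 for a single period. The masking works as intended.

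**Break showing a full sequence.** One design remains for each of the 24 orders that could be revealed. For example, P-M-L-H forces M-H-P-L, H-L-M-P and L-P-H-M on the other three groups. Any other participant with a known moxifloxacin period then has 1 possible order.

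**Break showing one blinded period.** There are 4 groups × 3 blinded periods = 12 blinded cells. The result depends on what is known of the unblinded participant's own moxifloxacin period.

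| Unblinded participant | Designs left | Best guess of another's order | Blinded cells fixed |
|---|---|---|---|
| Moxifloxacin period known | 2 | 1/2 | 4 of 12 |
| Not yet had moxifloxacin, period 1 shown | 6 | 1/6 | 0 |
| Not yet had moxifloxacin, period 2 shown | 4 | 1/4 | 0 |
| Not yet had moxifloxacin, period 3 shown | 2 | 1/2 | 4 of 12 |

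In the last row moxifloxacin must fall in period 4, so its period is deducible. With 2 designs left, the average best guess for a single blinded period is (4 × 1 + 8 × 0.5) / 12 = 67%. With 4 left it is 50%, and with 6 left 33%. If a participant unblinded in period 1 or 2 receives moxifloxacin later, the first row applies from then on.

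**Who is reached, and when.** Other participants' moxifloxacin periods become known only as they are dosed. After periods 1, 2, 3 and 4, one, two, three and four of the four groups are known. An early break reaches few groups; a late break leaves few assessments to influence.

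**What is reached.** Protocol Section 8.4.3 keeps the core-lab staff blinded to treatment, date, time and time point, and has each participant's intervals measured in random order. The QTcF values for the primary concentration-QTc analysis and for assay sensitivity do not pass through the site staff's knowledge of the sequence.

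**What a different list would gain and cost.** Take all 24 orders, shuffled in blocks of 24. After a full-sequence break, another participant in the same block with the same moxifloxacin period has 6 − 1 = 5 possible orders, a best guess of 20%, even if block boundaries are known. For others it stays at 1/6. Against that, balance holds only at completed blocks. Halfway through a block, the chance that placebo has been given equally often in all four periods is C(6,3)⁴ / C(24,12) = 160,000 / 2,704,156 = 5.9%. In simulated lists at an assumed N of 48, the placebo counts at 12 or 36 participants differed between periods by 4 or more in about 19%. The printed square can balance periods and first-order carryover at every completed set of four. The preparation team would also handle 24 orders instead of 4.

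**The case for a change.** The best case for a change is that the protocol itself treats open-label moxifloxacin as a threat to the blind, relies on letter masking as the remedy, and then prints the square that makes the masking depend on a single key. Section 6.3.2 says that only authorised staff will know the sequences used and that the Investigator stays blinded; one envelope could undo this for many participants. Safety and tolerability of evobrutinib is a stated secondary objective. A list can be changed cheaply before it is generated.

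The structural point stands: a full-sequence break does fix the order for every participant whose moxifloxacin period is known, and nothing visible in Sections 6.3.2 or 6.3.3 limits this. Three parts carry less weight:

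- The full-sequence case assumes something about envelope content that the documents do not state. The Unblinding Plan and Operations Manuals they mention are not available here, so containment at site level cannot be ruled out.
- The one-period case is partial, and it vanishes for a participant unblinded in period 1 before receiving moxifloxacin. That is realistic, because Section 7.1 names severe and serious adverse events as grounds for withdrawal from study intervention.
- The person who breaks the code need not make every later judgement. Sections 8.3 and 8.4.3 allow designees to record adverse events and evaluate ECGs.

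**Conclusion.** No change follows. The carry-over is real in principle, but it arises only after a code break, and the documents give no likelihood of one in this single-dose study of healthy participants. Its size ranges from no information (6 orders remain) to full knowledge of the order (1 remains), depending on envelope content and timing. It touches only later site assessments that feed secondary, descriptive tables. The core-lab QTcF measurements, and so the primary and assay-sensitivity conclusions, are protected separately.

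Replacing the square with 24 sequences would bring nothing unless a break occurs, and it would give up close period balance and simple preparation in every case. A sponsor's statistician could reasonably decline it. If the sponsor wants more protection, it can be settled in the preparation of the envelopes, by showing only the period concerned. By the table above, that limits the carry-over without removing it.

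This rests on the printed letters being the actual sequences under one key. The balance comparison also assumes a list built in sets of four, since the block size is not stated. The sample size is not visible, so N of 48 is only an illustration; the 5.9% applies halfway through any block of 24.
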